5.4. Administration and drug accountability

Study drugs (peginterferon alfa-2a, tenofovir DF, and emtricitabine/tenofovir) will be shipped to study sites from the drug distribution center. Staff at each site will be responsible for drug accountability. This will include documenting drugs received, study drug dispensed to participants, used and unused study drug returned, and accounting of any drug destroyed by the site. An accurate and up-to-date accountability log will be maintained by each site.

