6.5 End of Treatment (Week 192)

At week 192, all participants will complete the following:

1. Physical exam.
2. Assessment of adverse events, concomitant medications and adherence
3. Questionnaires (symptoms, quality of life, health behaviors, and fatigue)
4. Depression assessment.
5. Blood will be drawn for CBC, hepatic panel (including albumin, total protein, alkaline phosphatase), renal panel, serum uric acid, PT/INR, anti-HIV, qualitative HBeAg, anti-HBe, anti-HBs, HBsAg, and HBV DNA. A sample of blood will be

stored for eventual assessment of HBeAg and HBsAg concentration, precore/BCP analysis, and antiviral resistance testing.

6. A blood sample for storing serum and plasma for future research will also be drawn
7. Urinalysis and fasting urine creatinine and phosphate.
8. Ultrasound exam (if clinically indicated, per AASLD guidelines, done as standard of care).
9. Fibroscan if available and not performed at, or since, the week 180 visit

At week 192 (year 4), participants who meet study criteria for discontinuing therapy (section 6.5.1) will have treatment stopped.

6.5.1 Eligibility criteria for discontinuing treatment at week 192 (participants must meet all criteria)

Participants will be discontinued from treatment if they meet all of the following criteria as determined based on laboratory results at the week 180 visit and any additional test results and clinical assessment up until the week 192 visit:

1. HBV DNA <1000 IU/mL for the previous 24 weeks (i.e. starting at or before week 156 and continuing through week 180).
2. No cirrhosis (Ishak score 5 or 6) on baseline biopsy
3. Normal indices of liver function (CTP =5), albumin ≥3.8 g/dL, INR ≤1.3, direct bilirubin ≤0.5 mg/dL
4. No clinical evidence of decompensation
5. No clinical or radiologic evidence of portal hypertension
6. Platelet count ≥120,000/mm³
7. HBeAg-negative at baseline visit and confirmed at week 180, or HBeAg-positive at baseline visit with HBeAg loss at or before week 144 and confirmed at week 180. In either situation, there can be no HBeAg positive result at or after week 144.
8. HBsAg-negative (regardless of anti-HBe status), or if HBsAg-positive, HBeAg-negative and anti-HBe-positive at week 180

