6.14.2. Criteria for treatment reinitiation in the Post-Treatment Follow up Period

Tenofovir DF will be restarted for any one of the following:

- Any one of the three criteria: INR ≥ 1.3 , total bilirubin ≥ 3.0 mg/dL or direct bilirubin ≥ 1.0 mg/dL, regardless of HBV DNA or ALT level.
- Any clinical decompensation, regardless of HBV DNA or ALT level.
- HBV DNA $\geq 10,000$ IU/mL and ALT > 1000 U/L (male or female) (i.e. only one ALT value > 1000 U/L is needed to qualify).
- HBV DNA $\geq 10,000$ IU/mL and ALT ≥ 300 U/L for males, ≥ 200 U/L for females. A total of one HBV DNA $\geq 10,000$ IU/mL and any three ALT values ≥ 300 U/L (male) or ≥ 200 U/L (female) over the 4-week (or longer) time frame are needed to qualify. Treatment will be resumed if the third ALT remains ≥ 300 U/L (male) or ≥ 200 U/L (female).
- HBV DNA $\geq 10,000$ IU/mL and ALT ≥ 150 U/L for males or ≥ 100 U/L for females. A total of one HBV DNA $\geq 10,000$ IU/mL and any three ALT values ≥ 150 U/L (male) or ≥ 100 U/L (female) over the 12 week (or longer) time period are needed to qualify. Treatment will be resumed if the third ALT remains ≥ 150 U/L (male) or ≥ 100 U/L (female).
- HBsAg-positive and HBeAg-positive at week 192.
- HBsAg-positive, HBeAg-negative, and anti-HBe-negative at week 192

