6.14.3. Management after reinitiation of treatment

Participants who meet criteria for treatment reinitiation specified in section 6.14.2 will be restarted on Tenofovir DF 300mg daily. Tenofovir DF will be provided by the study until week 240. Monitoring of AST, ALT and HBV DNA levels will be done at 4, 8 and 12 weeks after Tenofovir DF is restarted and then every 12 weeks. If bilirubin or INR is abnormal at the time of treatment reinitiation, it (they) should be monitored at 4, 8, and 12 weeks after Tenofovir DF is restarted and then every 12 weeks until it (they) return(s) to normal. If, after treatment reinitiation, the participant meets criteria for non-response (section 6.9) or partial response (section 6.10), the drug therapy will be changed as outlined in those sections.

7. Adverse events and toxicity management

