Tenofovir DF has been associated with instances of lactic acidosis, but only in participants receiving other medications that have been associated with this complication, such as didanosine, stavudine and zidovudine. It is not clear whether tenofovir DF when used by itself or in combination with peginterferon alfa-2a, is associated with mitochondrial toxicity either to the liver (lactic acidosis, acute fatty liver and hepatic failure), muscle (myositis), nerves (neuropathy) or pancreas (acute pancreatitis).

In addition, all agents with activity against HBV replication carry a warning label about the risk of exacerbation of hepatitis after discontinuation of treatment. This issue is addressed by the protocol design and close follow-up of participants after stopping therapy (see section 6.6, 6.14.1, and Appendix 4).

7.3.b. Tenofovir DF and renal function

Tenofovir DF is principally eliminated by the kidney. Renal impairment, including cases of acute renal failure and a Fanconi-like syndrome (proximal renal tubular dysfunction with severe hypophosphatemia), has been reported.

Adverse Event Monitoring and Management Related to Elevated Serum Creatinine (Cr)
Nephrotoxicity will be based upon serum creatinine results:

- If Cr \geq 0.5 mg/dL above baseline, repeat testing within 72 hrs will be performed and drug continued unless the study physician considers drug discontinuation necessary.
- If Cr increases to \geq 1.2 mg/dL and by \geq 0.3 mg/dL from baseline, additional testing at the next scheduled visit should be considered (see Manual of Operations). If Cr \geq 1.2 mg/dL and $>$ 0.5 mg/dL above baseline on two consecutive occasions, the study drugs will be discontinued and not restarted unless another, reversible cause of creatinine elevations is identified. If the study physician identifies an alternative cause for the increase in Cr, study drugs may be resumed at discretion of study physician if calculated Cr clearance is $>$ 30 ml/min with tenofovir DF dose adjustment.
- Any study participant discontinued from the study will be recommended to commence anti-HBV therapy with an alternative HBV drug immediately (this drug will not be provided by the study).

Tenofovir DF Dosing is Based Upon Creatinine Clearance (CrCL)

Creatinine clearance will be calculated in all participants prior to initiating therapy and at each study visit to determine tenofovir DF dose.

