8.3. Safety analysis

8.3.1. Adverse events

Summaries of adverse events (number adverse events, number and percentage of participants with adverse events, rates per person-years) will be provided by treatment

group. Events will be summarized based on the date of onset for the event. A treatment emergent adverse event will be defined as an adverse event that begins on or after the date of first dose of study drug. Events that occur prior to the first dose of study medication or after the last dose of study medication will be summarized separately. Summaries of the following are planned:

- all adverse events recorded between screening and first dose of study medication,
- all treatment emergent adverse events,
- all emergent and related adverse events,
- all treatment emergent renal adverse events,
- all treatment emergent and related renal adverse events
- combined Grade 2, 3 and 4 treatment emergent adverse events,
- combined Grade 2, 3 and 4 related treatment and emergent adverse events,
- combined Grade 3 and 4 treatment emergent adverse events,
- combined Grade 3 and 4 related treatment and emergent adverse events,
- all adverse events that caused permanent discontinuation of study drug,
- all adverse events that caused temporary interruption of study drug,
- all serious adverse events, and
- all serious and related adverse events.

In addition quarterly safety analysis will be reported to DSMB.

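### Section 8.3.1 separates post-treatment adverse events by a single last-dose cut, which does not fit a design that stops and restarts tenofovir and tends to move the more serious withdrawal events out of that summary

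*Combined protocol and SAP*

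**What the plan says.** Section 8.3.1 allocates events by start date: "Events will be summarized based on the date of onset for the event". It then sets two boundaries. The first opens the treatment-emergent category: "A treatment emergent adverse event will be defined as an adverse event that begins on or after the date of first dose of study drug". No closing date is given. The second sets events aside at either end of dosing: "Events that occur prior to the first dose of study medication or after the last dose of study medication will be summarized separately". Thirteen planned summaries follow. One covers the time before the first dose; none is named for the time after treatment or off treatment.

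Tenofovir is a study drug under section 5.4: "Study drugs (peginterferon alfa-2a, tenofovir DF, and emtricitabine/tenofovir) will be shipped to study sites from the drug distribution center". At week 192, section 6.5 provides that "participants who meet study criteria for discontinuing therapy (section 6.5.1) will have treatment stopped". Section 6.14.2 lists the criteria for restarting it, among them "Any clinical decompensation, regardless of HBV DNA or ALT level". For those who restart, section 6.14.3 says "Tenofovir DF will be provided by the study until week 240". The text after 6.5.1 adds two further groups. Participants not eligible to stop continue study tenofovir to week 240. Participants who are eligible but choose to continue get no study drug after week 192 and must obtain treatment through standard care.

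**The concern.** A rule with one first dose and one last dose assumes a single continuous course. This protocol builds in a gap. When a participant stops at week 192, worsens and is restarted on study tenofovir, the last dose of study medication moves from week 192 towards week 240, and an event that began in the gap is no longer after it.

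Section 7.3.a notes that agents active against HBV carry a warning about the "risk of exacerbation of hepatitis after discontinuation of treatment", and says that the design and the close follow-up address it. The separate post-treatment summary is the natural place in the adverse event analysis to see that risk. If events followed by restart leave it while events without restart stay, the summary of withdrawal safety is thinned selectively.

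**Working it through.** The plan states no figure on this point, so the check compares texts and places events on the timeline.

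**Step 1: rule.** An event enters the separate post-treatment summary if its onset is later than the last dose of study medication (8.3.1). The section does not say which last dose applies when there are two courses. Two readings are possible:
- R1: the final dose ever taken, which is the literal reading.
- R2: the last dose of the first course.

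**Step 2: cases.** The stop and supply weeks are the protocol's; the onset and restart weeks are illustrative assumptions.

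| Case | Last study dose, R1 | R1: after last dose? | R2: after last dose? |
|---|---|---|---|
| Stop 192, flare 204, no restart | 192 | Yes | Yes |
| Stop 192, flare 204, study tenofovir 208 to 240 | 240 | No (204 < 240) | Yes (204 > 192) |
| Stop 192, flare 200, study tenofovir from 204, lost at 216 | 216 | No (200 < 216) | Yes (200 > 192) |
| Stop 192, flare 236, criteria met at 240 when supply ends | 192 | Yes | Yes |
| Eligible to stop but on non-study tenofovir, event 210 | 192 | Yes, although treated | Yes, although treated |

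The first two rows are the same event with the same onset. Only the later restart changes where it is shown under R1.

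**Step 3: which events are followed by restart?** Section 6.14.2 restarts tenofovir for clinical decompensation; for INR of at least 1.3, total bilirubin of at least 3.0 mg/dL or direct bilirubin of at least 1.0 mg/dL; and, with HBV DNA of at least 10,000 IU/mL, for one ALT above 1000 U/L or for sustained lower ALT elevations. Restart is therefore related to severity, and so is the loss from the summary.

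**Step 4: does R2 repair the rule?** No. Under R2 an event during restarted treatment, say at week 220, counts as after the last dose (220 > 192) although the participant is on tenofovir. The last row of the table is misplaced under both readings.

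**Step 5: size.** If F withdrawal flares occur and a share r is restarted on study tenofovir before week 240, F × r leave the summary under R1. The documents give neither F nor r. With F = 30 assumed:
- r = 10%: 30 × 0.10 = 3 leave, 27 stay.
- r = 30%: 30 × 0.30 = 9 leave, 21 stay.
- r = 50%: 30 × 0.50 = 15 leave, 15 stay.
- r = 80%: 30 × 0.80 = 24 leave, 6 stay.

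**The case against.** The best defence is that the protocol elsewhere ties the end of treatment to week 192: the 192-week regimens in 5.1, the title of 6.5, the off-treatment analyses in 8.1.2.1 and the column labels of Appendix 4. On that reading the flares stay in the summary. This shows that the text is ambiguous rather than explicit, and that stands. It does not rescue the rule: ineligible participants take study tenofovir to week 240, and post-restart events would be classed as post-treatment (Step 4).

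A second defence is that withdrawal safety is covered elsewhere. Section 6.14.1 defines virological relapse, biochemical relapse and ALT flare for use in data analyses, and the stopping rule in 9.1 counts clinical decompensation whatever the adverse event window. This stands in part. No endpoint in 2.2 and no analysis in section 8 names relapse or flare. Both relapse definitions need two samples at least 12 weeks apart, one of them at or beyond about 24 weeks after stopping, so an early restarter who is re-suppressed may meet neither. The flare definition misses decompensation or bilirubin and INR events at lower ALT. Section 7.6.1 does not count hepatic decompensation as a serious adverse event, so the serious-event tables would not show it on that ground. The stopping rule governs conduct, not final reporting.

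Stronger readings that a reader might infer do not hold:
- That every severe withdrawal event is lost. A flare whose restart falls at week 240 or uses non-study drug stays in.
- That these events are filed as on-treatment and inflate on-treatment toxicity. Section 8.3.1 has no such category. The treatment-emergent definition has no end, so restart does not change that count.
- That restart cleanly separates severe from mild. One ALT above 1000 U/L with HBV DNA below 10,000 IU/mL does not by itself trigger restart, whereas two criteria are week-192 serology results with no clinical event.
- That endpoint 2.2.9 is biased between arms. It carries no window, and counting withdrawal events in the randomised arm where they arise is a legitimate comparison of strategies.

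**Conclusion.** The concern holds as a defect in the allocation rule. On the literal reading of last dose, events that begin off drug and are followed by restart on study tenofovir before week 240 drop out of the separate post-treatment summary, and the restart criteria make that loss fall more on the serious events. On the alternative reading the rule misplaces other events instead. Left as it is, the choice between readings could be made after the data are seen.

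The number affected cannot be derived from the documents; the 3 to 24 of 30 above only shows how the result depends on the restart share. Any distortion between arms in the post-treatment summary requires the arms to differ in how many participants stop or restart. The point warrants a change to the analysis plan and does not touch the primary endpoint.

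**What to change.** In 8.3.1, replace the last-dose cut with windows assigned by onset date:

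- (a) First course: from the first dose to week 192, to an earlier stop, or to week 240 for those not eligible to stop who continue.
- (b) Off treatment: from that stop to the day before any restart, or to the end of follow-up.
- (c) After restart: from the restart to the end of follow-up.

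Apply the listed summaries by arm within each window, with that window's own participants and person-years as denominators. State that time on non-study antiviral therapy after the stop of study drug is not off-drug time in (b). This covers eligible participants who continue through standard care and those stopped early under 7.3.b who are advised to start another drug. Keep the comparison of all events by arm for endpoint 2.2.9.

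The cost is SAP wording and a few extra tables. Restart timing must already be known, because 6.14.3 schedules monitoring at 4, 8 and 12 weeks after it, and 5.5 records concomitant medication at each visit, which should identify non-study antivirals. The downside is that off-treatment rates rest on fewer person-years and are less precise. Clinical management does not change.

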8.3.2. Laboratory abnormalities

Laboratory results will be presented as both actual value as well as a function of normal range. Selected laboratory data (using conventional units) will be summarized by the change from baseline in laboratory test. If baseline data are missing, then any graded abnormality is considered treatment emergent.

8.3. Sample size and power

The sample size for this study was determined based on the primary endpoint of HBsAg-loss at 48 weeks after treatment has been stopped. There are no data available on HBsAg loss for long-term treatment with tenofovir DF or tenofovir DF and peginterferon combination therapy. We anticipate that after 192 weeks of treatment and 48 weeks of follow-up post-treatment 5% of the participants in the tenofovir DF alone group will achieve HBsAg loss compared to 15% participants in the tenofovir DF and peginterferon combination therapy group. The clinical trial would require 141 participants per arm (282 participants in total) to detect this expected difference with 80% power at 5% level of significance using a two-sided test of equality between two proportions (chi-square test). However, for this long-term treatment trial, it is expected that approximately 25% of the participants will be lost to follow-up and hence the study will recruit a total of 376 participants (randomized 1:1 to two treatment arms, 188 per arm) to account for the missing participants.

9. Data and safety monitoring board

Data and safety will be monitored by the NIDDK in conjunction with an NIDDK-appointed Data and Safety Monitoring Board (DSMB). This board serves in a consultative capacity to inform the NIDDK decisions regarding conduct of the study. The description of DSMB activities is included in the DSMB Charter.

9.1 Data and safety monitoring plan

This phase III randomized trial aims to compare the long-term efficacy of initial treatment with combination therapy with peginterferon plus tenofovir DF versus tenofovir DF monotherapy in the treatment of chronic hepatitis B. The individual drugs (peginterferon and tenofovir DF) are FDA-approved and have been well-studied. The risks to participants are outlined in sections 5.2.3 and 5.3.3 in the accompanied protocol. Section 7 of the protocol defines the toxicities associated with these drugs and outlines dose adjustment and discontinuation guidelines due to toxicity.

Emtricitabine/tenofovir DF coformulated as a single tablet Truvada is approved for HIV but not for HBV treatment. Emtricitabine/tenofovir DF will be offered to patients who have primary nonresponse, partial virologic response or confirmed virologic breakthrough. Adverse events and dose adjustment guidelines are described in section 7.4.

The data and safety monitoring plan (DSMP) for this study focuses on close monitoring by the principal investigators (PI) and prompt reporting of excessive adverse events and all serious adverse events to the DCC and the appropriate oversight committees or entities such as the NIDDK, the Data and Safety Monitoring Board (DSMB) and to the participating centers' IRB/REBs.

The Data Coordinating Center (DCC) will monitor clinical center performance (e.g., recruitment, retention, data completeness, timeliness of data collection and submission) and protocol compliance. These reports, with summaries of adverse event data, will be provided to the DSMB for their quarterly reports and biannual calls or meetings, and to the Steering Committee at its annual meeting. DSMB reports will include both open and closed session reports, with only the latter including information by treatment arm.

The DCC will work with the Safety Officer and the Steering Committee to maintain a cumulative summary of adverse events (overall and stratified by serious/non-serious status) that will be forwarded to the DSMB every three months. Safety reports will also be sent to the Principal Investigators and the NIDDK Project Officers. The Project Coordinator will be responsible for distributing these reports and assuring that all parties obtain copies of these reports.

The frequency of data review for this study differs according to the type of data and can be summarized in the following table:

Data type	Frequency of review
Recruitment Retention Protocol adherence(e.g., meeting inclusion/exclusion criteria, treatment compliance) Pregnancy and outcomes in female participants	Quarterly reports for NIDDK and the appropriate oversight committees
Adverse events and Serious Adverse Events (SAE) that do not meet expedited reporting criteria	Quarterly reports for NIDDK and the appropriate oversight committees
Serious Adverse Events that meet expedited reporting criteria*	As they occur for NIDDK, DSMB, appropriate industry partner(s), and

	cumulative reports quarterly
Laboratory data	Yearly for the DSMB

The definition of adverse and serious adverse events is provided in section 7.6.1 of this protocol along with the reporting procedures in the MOP.

Stopping rules during the treatment phase (up to Week 192)

No interim analysis for efficacy is planned for this clinical trial, since the primary endpoint is expected to occur very rarely during the treatment period. As mentioned above, adverse event reporting will be quarterly throughout the study. Additional analyses will be performed at the recommendation of the DSMB if there are any concerns raised by adverse events or serious adverse events reported. The following study-wide stopping rules have been agreed upon by the clinical investigators for this interim analysis. The study will be stopped if at least one of the following occurs:

1. If the incidence of renal toxicity (defined as a persistent increase in serum creatinine >1.0 mg/dL above baseline on two successive visits 4 weeks apart or persistent grade 3 or grade 4 hypophosphatemia (requiring TDF discontinuation) exceeds 10% in either of the two study arms.
2. If the incidence of peripheral neuropathy (documented by EMG) exceeds 10%.
3. If the incidence of grade IV toxicity exceeds 10% in either of the two study arms.

Stopping rules during treatment discontinuation phase (Weeks 192 to 240)

The following has been agreed upon by the clinical investigators

1. If more than 1 participant develops clinical decompensation, no further participants will undergo treatment withdrawal until the formal review by investigators and the DSMB
2. Resumption of treatment withdrawal may occur if the DSMB and investigators determine the safety measures are adequate AND that the benefits of continued study of treatment withdrawal outweighs the risks

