6.4. On-Treatment assessments

After randomization, participants will be seen in follow up at 4-week intervals for the first 12 weeks and then at 12 week intervals until therapy is completed, as shown in the Time and Event Chart (Appendix 3). For participants having side effects related to treatment or adherence issues, more frequent visits can be undertaken at the discretion of the study physician. These visits will be conducted as an “Unscheduled Visit” and tests/procedures performed will be at the discretion of the study physician (with the exception of adverse events to be managed per guidelines specified in the protocol or manual of operations, i.e. hepatitis flare or hypophosphatemia).

1. Each outpatient visit will include assessment of compliance, adverse events reporting, vital signs, weight, symptoms evaluation, record of concomitant medications, drug dispensing, and blood testing as detailed in the Time and Event Chart (Appendix 3).
2. Symptom questionnaire at each visit.
3. Depression assessments at weeks 12, 24, 36, 48, and 96.
4. Fatigue questionnaire at weeks 24 and 96.
5. Health Behavior and quality of life questionnaires at weeks 48, 96, and 144.

6. Blood will be drawn for CBC with differential at each visit until week 36 and then CBC without differential at week 48, 96, and 144.
7. Hepatic panel (AST, ALT, total bilirubin) at each visit.
8. A renal panel (creatinine, calculated creatinine clearance, phosphate, blood urea nitrogen, and calcium) at every visit from week 12 on.
9. TSH at weeks 12 and 24.
10. Glucose and triglycerides at week 24.
11. There will be a PT/INR, serum uric acid, and other liver tests (albumin, total protein, alkaline phosphatase, direct bilirubin) at weeks 48, 96, and 144.
12. There will be a urinalysis done at weeks 48, 96, and 144.
13. A fasting urine creatinine and phosphate will be done at week 96.
14. For females of childbearing age, adherence to contraception will be reviewed and a pregnancy test repeated at each visit during the peginterferon treatment phase.
15. Qualitative HBeAg (in patients who were HBeAg-positive at baseline visit) and HBsAg at weeks 48 and 96. If there is HBeAg or HBsAg loss then anti-HBe or anti-HBs will be tested.
16. Qualitative HBeAg and anti-HBe (regardless of HBeAg status at the baseline visit) at weeks 144 and 180.
17. Qualitative HBsAg at week 180.
18. Quantitative HBsAg and HBeAg will be tested at every visit from week 12 on.
19. HBV DNA will be drawn at every visit.

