6.8. Management of non-response

Definition: Primary non-response is defined as a failure to achieve a $>1\text{-log}_{10}$ IU/mL decline in HBV DNA after the first 24 weeks of treatment. HBV DNA will be measured by the quantitative HBV DNA assay which will be reconfirmed with re-testing 4 weeks later (week 28). Compliance with study medications will be assessed and documented. Primary non-response is considered to be treatment failure.

Management of non-response

- 6.9.1.** Reinforce compliance when non-response is initially suspected.
- 6.9.2.** Testing of Tenofovir DF levels may be performed (samples will be archived for analysis and not available in real-time).
- 6.9.3.** If serum HBV DNA report confirms that participant meets criteria for virological non-response, change to combination emtricitabine/tenofovir within 2 weeks of obtaining the week 28 result.
- 6.9.4.** Participants will be assessed at weeks 4, 8 and 12 and then every 12 weeks after initiation of rescue therapy to document the response. Thereafter, participants will be followed per protocol.

6.9.5. If serum HBV DNA is ≥ 1000 IU/mL by HBV DNA quantitation assay after 24 weeks of rescue therapy, subsequent treatment will be altered at the discretion of the study physician.

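### Two section 9.1 stopping rules do not fit the tests and reporting routes stated elsewhere: four-week creatinine pairs are not routinely drawn, and non-fatal decompensations have only a quarterly timetable

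*Combined protocol and SAP*

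**What the plan says.** **Renal rule.** In section 9.1 the study stops, during treatment, if renal toxicity exceeds 10% in either arm. Renal toxicity is "defined as a persistent increase in serum creatinine >1.0 mg/dL above baseline on two successive visits 4 weeks apart", or persistent grade 3 or 4 hypophosphatemia that leads to tenofovir being stopped.

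**Creatinine tests on treatment.** Section 6.4 sees participants "at 4-week intervals for the first 12 weeks and then at 12 week intervals until therapy is completed". Its item 8 orders "A renal panel (creatinine, calculated creatinine clearance, phosphate, blood urea nitrogen, and calcium) at every visit from week 12 on". Section 7.3.b is broader: "Creatinine clearance will be calculated in all participants prior to initiating therapy and at each study visit to determine tenofovir DF dose". That wording would add weeks 4 and 8.

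**Response to a rise.** For a rise of at least 0.5 mg/dL, section 7.3.b says "repeat testing within 72 hrs will be performed and drug continued unless the study physician considers drug discontinuation necessary". For a level of at least 1.2 mg/dL that is also more than 0.5 mg/dL above baseline, it says "on two consecutive occasions, the study drugs will be discontinued and not restarted unless another, reversible cause of creatinine elevations is identified".

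**Creatinine tests off drug.** Early stoppers have the week 192 assessments, which include a renal panel (sections 6.13.2 and 6.5). Those stopping for an adverse event then follow Appendix 4. Section 6.6 requires the renal panel at those visits for participants on tenofovir; the Appendix 4 footnote requires it for participants on treatment. Creatinine is required of everyone only at week 240.

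**Decompensation rule.** From week 192 to 240, section 9.1 halts further withdrawals once more than one participant has clinical decompensation, until investigators and the DSMB have reviewed the matter. Section 7.6.1 excludes hepatic decompensation from serious adverse events. The 24-hour routes in section 7.6.3 cover deaths and unexpected, drug-related serious events. Sections 8.3.1 and 9.1 send other adverse event data onward quarterly.

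**The concern.** A stopping rule works only if the protocol generates the data it counts, and moves them fast enough for the rule to act.

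The creatinine part of the renal rule needs two values four weeks apart. The routine schedule almost never produces such a pair, and a creatinine rise leads to a much shorter repeat and then to stopping drug. A participant taken off drug for a confirmed rise might thus never meet the definition that is meant to count that harm, and the 10% limit could be reached later than intended.

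The decompensation rule is a count across sites with a trigger of two, while each site's investigator reconfirms stopping at week 192 (section 6.4.1). If the second case is not passed on promptly, other sites have no stated way of knowing that withdrawals should pause.

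These are the trial-level guards against tenofovir nephrotoxicity and against harm from withdrawal.

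**Working it through.** The plan states no figure for either point, so there is none to reproduce. The counts below come from its schedules.

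**1. Routine pairs on treatment**

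- Section 6.4, item 8: panels at weeks 12, 24, ..., 192. Number of panels = (192 − 12)/12 + 1 = 16, so 15 successive gaps, all of 12 weeks. Four-week pairs: **0 of 15**.
- If section 7.3.b governs, weeks 4 and 8 are added: 18 values, 17 gaps. Four-week pairs: **2 of 17** (weeks 4–8 and 8–12).
- On either reading there are none from week 12 to week 192, which is 180/192 = 94% of the treatment period.
- The day 0 value is left out because it is the baseline against which the rise is measured.

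**2. What a qualifying rise triggers**

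A value more than 1.0 mg/dL above baseline is also at least 0.5 above it, so the 72-hour repeat applies. For any baseline of 0.2 mg/dL or more, the level is above 0.2 + 1.0 = 1.2 mg/dL. A confirmed repeat therefore also meets the section 7.3.b stopping criterion. The pair so produced is about three days apart, not four weeks. (Section 7.3.d words the creatinine criterion differently from 7.3.b. That needs its own reconciliation; the pair counts in step 1 do not depend on it.)

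**3. After drug is stopped**

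The stop visit plus post-treatment weeks 4, 8, 12, 16, 20, 24, 36 and 48 give 8 gaps, of which 6 are four weeks. Whether creatinine is required at both ends depends on the reading:

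- If the panel is only for those on tenofovir (section 6.6), none of the 6 gaps has a required creatinine at both ends for someone off it.
- If being on treatment (Appendix 4) includes another antiviral, participants who start one would have the panel at each visit.

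The two passages differ and the text does not settle which holds.

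**4. Scale of the renal rule**

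Planned arm size is 376/2 = 188 (sample size section). Ten percent is 18.8, so the rule trips at 19 participants in an arm. The documents give no share of qualifying participants who would lack a four-week value, so the undercount cannot be sized.

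**5. Reporting routes for the decompensation rule**

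| Event | Route to the DCC | Onward |
|---|---|---|
| Unexpected, related serious event | 24 hours (7.6.3) | Expedited, including clinical centers |
| Death | 24 hours (7.6.3) | Immediate, including clinical centers |
| Non-fatal hepatic decompensation | Adverse event form, no deadline (7.6.2) | Quarterly (8.3.1, 9.1) |

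A quarter is 52/4 = 13 weeks, and 13/48 = 27% of the withdrawal phase. This is the upper end of the onward lag on the stated timetable.

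**The case against.** **Other visits can supply a four-week creatinine.** Section 6.4 allows unscheduled visits for treatment side effects, which would cover nephrotoxicity. Flares are seen every four weeks (6.12), and breakthrough and non-response are retested at four weeks (6.8, 6.11). On rescue, "Participants will be assessed at weeks 4, 8 and 12 and then every 12 weeks after initiation of rescue therapy", and section 7.4 calculates clearance at each visit for Truvada dosing. Unresolved adverse events are followed (7.6.2). All of this stands, so pairs will exist for some participants. But the unscheduled visits and their tests are discretionary, the flare, retest and rescue visits are prompted by ALT or HBV DNA, and adverse event follow-up sets no interval. None clearly requires a four-week value because creatinine rose.

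**Text that cannot be seen may settle it.** The renal row of Appendix 3 is not in the text available. Its footnote 3, to follow an abnormal result until it normalizes, may or may not attach to that row. Section 7.3.b also refers to the Manual of Operations for creatinine follow-up. This limits confidence in the renal part.

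**The harm would still be visible.** Section 8.3.1 summarizes renal adverse events and discontinuations due to adverse events, with quarterly safety analysis to the DSMB, and section 9.1 allows extra analyses. This stands. Those tables do not apply the section 9.1 definition, however. The review table lists laboratory data as yearly for the DSMB, and nothing says which source feeds the count.

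**The decompensation part is silence, not contradiction.** Excluding an event from serious adverse events is compatible with a trial-level pause, and the mechanics are left to the Charter and the Manual. Section 9.1 also promises prompt reporting of excessive adverse events. This is fair as far as it goes, but neither promptness nor excess is defined, and no supplied text gives a trigger of two a timed route.

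**Conclusion.** Both parts hold, within limits.

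1. The creatinine count in section 9.1 cannot be computed reliably from the creatinine tests that the supplied text requires: 0 of 15 routine pairs qualify, or 2 of 17 on the broader reading. It can miss participants taken off drug for confirmed rises. The hypophosphatemia part of the rule, the neuropathy rule and the grade IV rule are not affected.
2. For non-fatal decompensation, the only stated onward timetable is quarterly: up to about 13 weeks, or 27% of the withdrawal phase.

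A reader might infer that the renal rule can never trip on creatinine, or that nephrotoxicity would go unnoticed. The documents do not support that: non-routine visits can supply pairs, hypophosphatemia cases count toward the same 10%, and confirmed cases should appear in quarterly summaries. A reader might also infer that sites would go on withdrawing treatment for a quarter after a second decompensation, or try to count those withdrawals. The Manual of Operations and Charter may give a faster route, and the documents state neither the share eligible to stop nor the length of enrolment. Only the possible lag can be stated.

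The conclusion assumes that sections 6.4 and 7.3.b reflect the unseen Appendix 3 row, and that no faster route exists in the documents not supplied.

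**What to change.** **Renal count.** Reconcile the section 9.1 definition with sections 6.4, 6.6 and 7.3.b and Appendix 4, so that the count can be computed from tests the protocol requires. Thresholds, timing and who is counted are for the investigators to choose. Report the counts behind the stopping rules in the existing quarterly DSMB report.

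**Decompensation pause.** In section 7.6.3, have each clinical hepatic decompensation in weeks 192 to 240 reported to the DCC and passed on to the DSMB and clinical centers as it occurs, by the existing expedited route and whatever its serious-event status. Alternatively, cite in section 9.1 the Manual of Operations or DSMB Charter text that already does this; if it exists, that citation closes this part.

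**Cost.** Protocol wording, a few more expedited reports and slightly longer quarterly reports.
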